9.6.4.3 Safety Analysis

Adverse events (AE) will be presented by seriousness, severity and relation to study device. The primary safety variable, the cumulative incidence (and 95% CI) of device-related adverse events (AEs) and SAE's observed throughout the follow-up period, will be presented in a tabular format. A detailed list of all adverse events will be presented. The adverse event rate will be compiled with respect to frequency, nature, severity of the event, and relationship to the study device. In addition, listings of all safety measures will be provided.

The rate of SAE's, if any, associated with use of PregSense™ is expected to be very small.

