Medical Device Description:	
PregSense™, developed and designed by Nuvo Group, consists of the following three basic components:
 
 (1) Wearable device – containing; 
 a. The sensors module (WSB- Wearable Sensory Belt) b. The major electronic module (WSH - Wireless Sensing Hub) (2) Mobile Application (MA) – 
 a. Gateway Service Application b. Presentation Application: 
 i. MD Application: ii. ME Application: (3) Cloud based application 
PregSense™ will include the following features [Please note, in PregSense Apps (ME, MD or Pivotal Study App) the features might be presented in alignment with the end user requirements]:
 
 • FHR (Fetal Heart Rate) • MHR (Maternal Heart Rate) • Fetal heart rate response (Fetal Activity) (in PregSense ME App) • Maternal Activity (in PregSense ME App) • Uterine Activity (Uterine Contractions, if applicable) 
Note: For this Pivotal study, a subversion of the Application with study metrics only will be applied, in order to show the agreement between PregSense and the standard of care device (i.e. CTG).

Study Endpoints:	
Primary Performance Endpoints:
 
 • Fetal HR

**CLINICAL STUDY EVALUATING THE SAFETY OF THE NON-INVASIVE
PRESENSE™ AND COMPARATIVE PERFORMANCE OF PRESENSE™
VERSUS CTG INPRENATAL MONITORING OF PREGNANT SUBJECTS**

Ref. No.: CLP1000

Rev. 05

Page 10 of 42

- Maternal HR

Safety Endpoints:

- Safety, tolerability and compliance with PregSense™ in pregnant women with singleton pregnancy > 32 + 0 weeks of gestation.
- All adverse events and serious adverse events related and unrelated to PregSense use.

As collected via PregSense™ and the data collected via the standard of care monitoring system (i.e. CTG).

Secondary Performance Endpoints:

- Uterine contractions

As collected via PregSense™ and the data collected via the standard of care monitoring system (i.e. CTG).

LIST OF ABBREVIATIONS

ACOG - American College of Obstetricians and Gynecologists
ADR – Adverse Device Reaction
AE – Adverse Event
APP - Proprietary Mobile Application
BMI – Body Mass Index
BT- Bluetooth
CCM - Cloud Computing Module
CE - European Conformity
CL – Cervical Length
CRC – Clinical Research Coordinator
CRF – Case Report Form
CTG – Cardiotocography
DPE - Data Processing Engine

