4 STUDY ENPOINTS

4.1 Primary Performance Endpoints:

The primary performance endpoints will include:

- Fetal HR

Maternal HR Both endpoints will be collected via PregSense™ and via the standard of care monitoring system (CTG).

4.2 Safety endpoints:

Incidence of device related and/or protocol procedure related adverse events and/ or serious adverse events related to the study device, in pregnant women with singleton pregnancy > 24 + 0 weeks of gestation.

4.3 Secondary Performance Endpoints:

The secondary performance endpoints will include:

- Uterine contractions

PregSense™ also acquires and displays the UA (Uterine contractions) tracing from the uterine Electrohysterography (EHG) signal.

Contractions will be collected via PregSense™ and via the standard of care monitoring system (CTG).

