5.1.2 Recording session

The primary objective is to assess the agreement between the PregSense™ device data collection, and the values as measured via the standard of care used for prenatal monitoring (i.e. CTG).

First, the authorized study personnel will register the subject into the App. If the subject is already registered, the subject's study I.D number will be entered to the App.

PregSense™ WSB then will be applied by the authorized study personnel to the maternal abdominal area of the subject after cleaning the maternal abdomen with a damp cloth, then drying the abdomen. Before initiating the recording session, a valid signal should be obtained. Therefore, a 2 minutes signal validation test will be executed. If validation test fails, re-adjustment of the PregSense™ WSB connections and placement should be re-validated, then another validation test will follow (if validation test does not pass after three adjustments the subject shall be excluded).

Once the validation test has passed, a 10-minute session will be recorded.

After session completion, the authorized study personnel will apply the CTG transducers, and will confirm fetal heart rate detection according to the standard of care procedure.

If a valid signal is detected, a new 30-minute session will be initiated recording both systems simultaneously in a synchronized method (PregSense™ and CTG).

Following the completion of the sessions, the nurse/clinician will remove both monitoring systems from the maternal abdomen.

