8.2.2 Relationship of an adverse event to the Treatment/ Device

- Unrelated: The AE has no temporal relationship to study device, and/or there is evidence of alternative cause such as concurrent medication or illness.
- Possibly related: A temporal relationship with study device is not clear, alternative causes are also possible.
- Probably related: A clear cut temporal relationship to the use of study device and potential alternative etiology is not apparent.
- Definitely related: A clear cut temporal relationship to the use of study device and no other possible cause.

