9.2.2 Safety Endpoint Measures

Incidence of device related and/or protocol procedure related adverse events and/or serious adverse events related to the study device, PregSense™, in pregnant women with a singleton pregnancy > 24 +0 gestational weeks.

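### The primary safety variable in section 9.6.4.3 omits the procedure-related events that sections 4.2 and 9.2.2 put in the safety endpoint, and its follow-up period is undefined

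*Combined protocol and SAP*

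**What the plan says.** The safety endpoint is defined in four places.

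- Study Synopsis, Study Endpoints: "All adverse events and serious adverse events related and unrelated to PregSense use".
- Section 4.2: "Incidence of device related and/or protocol procedure related adverse events and/ or serious adverse events related to the study device".
- Section 9.2.2: "Incidence of device related and/or protocol procedure related adverse events and/or serious adverse events related to the study device, PregSense™".
- Section 9.6.4.3, which names the primary safety variable: "the cumulative incidence (and 95% CI) of device-related adverse events (AEs) and SAE's observed throughout the follow-up period". The interval and the form of reporting are given only as "observed throughout the follow-up period, will be presented in a tabular format". The same section tabulates AEs by seriousness, severity and relation to the device, and promises a listing of all AEs.

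On causality, section 8.2 asks the investigator to judge each event's relationship to the investigational device. Section 8.2.2, headed "Relationship of an adverse event to the Treatment/ Device", gives four categories, each worded in terms of the study device.

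On the period of observation, the synopsis expects up to 2 hours per subject and allows optional further sessions up to labor. Section 5.1.2 ends the procedure thus: "Following the completion of the sessions, the nurse/clinician will remove both monitoring systems from the maternal abdomen". Section 8.3 applies AE reporting to events at any time in the trial, without a start or stop for the individual subject.

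**The concern.** Section 9.6.4.3 is the only section that says what will be computed, and its numerator differs from the endpoint it is meant to report. An event caused by a study procedure but not by the device counts under 4.2 and 9.2.2 and does not count under 9.6.4.3. It is also unclear whether SAEs in 9.6.4.3 must be device-related; 4.2 and 9.2.2 say they must.

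Safety is part of the stated primary objective in the synopsis and of the study purpose in section 9.1. If the text stays as it is, the analyst has to choose a numerator when the data are already in hand, and one of the candidates has no causality data specified to support it. A cumulative incidence also needs a stated interval, and the interval named here is not defined.

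**Working it through.** The documents give no expected safety rate, margin or safety sample size, so there is no figure of the plan's to reproduce. The check is a comparison of passages, with an illustration of what the choice of numerator can do.

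**1. Numerators side by side**

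- (a) Synopsis: all AEs and SAEs, any cause.
- (b) Sections 4.2 and 9.2.2: AEs related to the device or to protocol procedures, and device-related SAEs.
- (c) Section 9.6.4.3: device-related AEs, and SAEs with the attribution left open.

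For AEs, (c) is a subset of (b), and (b) is a subset of (a). The difference between (b) and (c) is the procedure-related-only group. For SAEs, (c) could be wider than (b) if unrelated SAEs are counted.

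**2. What the specified data can recover**

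- All-AE count: yes, from the full listing.
- Device-related count: yes, from the 8.2.2 grading and the tabulation in 9.6.4.3.
- Procedure-related count: no. Neither 8.2 nor 8.2.2 specifies a procedure-relatedness judgement, so an event graded unrelated to the device could be procedure-related or not.

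The sponsor does recognise the distinction. Section 3.6.2 reports the feasibility study (76 subjects, 510 sessions) as free of both procedure-related and device-related events.

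**3. Size of the numerator effect**

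Let d be the number of subjects with a device-related event, p the number whose only related event is procedure-related, and N the size of the safety set. Taking SAEs as device-related in both, (b) − (c) = (d + p)/N − d/N = p/N. One such subject is worth 1/50 = 2.0 percentage points at the minimum recruitment of 50 (section 9.4) and 1/200 = 0.5 at the maximum of 200 (synopsis).

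Illustration with assumed counts, which are not in the documents: d = 2, p = 2, and 4 more subjects with unrelated events only. Exact 95% limits are the 0.025 quantile of Beta(x, N − x + 1) and the 0.975 quantile of Beta(x + 1, N − x).

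- N = 50: (c) 2/50 = 4.0% (0.5 to 13.7); (b) 4/50 = 8.0% (2.2 to 19.2); (a) 8/50 = 16.0% (7.2 to 29.1).
- N = 200: (c) 2/200 = 1.0% (0.1 to 3.6); (b) 4/200 = 2.0% (0.6 to 5.0); (a) 8/200 = 4.0% (1.7 to 7.7).

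With x = 0 throughout, all three give 0%.

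**4. Observation window side by side**

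The follow-up period appears only in 9.6.4.3. The other candidates for the interval are the 2-hour expectation and the optional sessions up to labor (both synopsis), removal of the monitors at session end (5.1.2), and reporting over the whole trial (8.3). They do not describe the same interval, and nothing says which one 9.6.4.3 means. With optional sessions, observed time can also differ between subjects, and the plan does not say whether incidence is per subject or per session.

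**The case against.** Much of the numerator problem is softened by section 9.6.4.3 itself. Because AEs are shown by relation to the device and listed in full, a reader can rebuild the all-AE and device-related counts. If no events occur, as in the feasibility study, the definitions agree numerically. The AE form is not among the documents, so it may hold a procedure item that the protocol does not mention. Safety is not part of the success criterion in 9.3. All of this stands. It confines the loss to the procedure-related subset and to the interpretation of the safety report, but it does not make the computed variable match the endpoint.

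A reader might infer more from the window: that the study has no follow-up at all, that observation stops when the belt comes off after about 2 + 10 + 30 = 42 minutes, and that later skin reactions go unobserved. The documents do not support this. Further sessions up to labor are allowed, section 8.3 extends reporting over the trial, and section 8.1 asks for duration, resolution and outcome of each event. The 42 minutes adds only one validation test and two recordings. It leaves out placement, readjustment, CTG application and any later session, against a stated figure of up to 2 hours. The window is undefined; it is not shown to be absent.

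A reader might also take the zero-event upper limits, 1 − 0.025^(1/N) = 7.1% at 50 and 1.8% at 200, as the size of the defect. The arithmetic is right, but the limits are the same under every numerator and so reflect sample size only.

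**Conclusion.** The point holds for the numerator. The primary safety variable in 9.6.4.3 is not the endpoint of 4.2 and 9.2.2, nor that of the synopsis, and the procedure-related part cannot be derived from the assessments the protocol specifies. The mismatch in definition is certain; the mismatch in the reported number depends on the events. It is p/N for subjects whose only related event is procedure-related, and zero if there are none. The 4%, 8% and 16% at 50 subjects rest on assumed counts and show only that the choice can matter. The result also assumes that the AE form collects no more than sections 8.2 and 8.2.2 describe.

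The window is a lesser, secondary defect: an undefined term that must be reconciled with the other passages. It is not evidence that later events go unobserved. The performance decision in 9.3 is unaffected. The change should be made because it is cheap and because causality not judged at the time is hard to reconstruct later.

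**What to change.** - Use the 4.2/9.2.2 numerator (device- or procedure-related) in 9.6.4.3 and in the synopsis, and list unrelated events separately.
- State in every place whether SAEs must be device-related to count.
- Add a relationship-to-procedure item to the AE assessment in 8.2 and 8.2.2 and to the AE form.
- Reconcile 9.6.4.3 with the synopsis, 5.1.2 and 8.3 so that the AE observation window has one stated meaning, including optional sessions, and say whether incidence is per subject or per session. Limit the safety conclusion to the interval actually observed. Simply ending the variable at belt removal would not reconcile the text, because it could exclude later related events that 8.3 requires to be reported.
- While these sentences are open, reconcile the gestational age in 4.2 and 9.2.2 (above 24+0 weeks) with the eligibility criterion in 6.1 (above 32+0 weeks).

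The cost is protocol and SAP wording and one form field. The reported related-event incidence may be slightly higher.

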9.6.5 Pooling

Poolability of the study centers will be evaluated by comparing the demographic and baseline parameters between the centers by data type. If the differences between the centers are found significant, the reasons for these differences will be further explored and rationalized with reference to the effect on the main performance parameters.

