16 REFERENCES42

Table of figures:

Figure 1 PregSense ME (self-monitoring)..... 15

Figure 2 PregSense MD (remote monitoring)..... 16

Figure 3 PregSense MD (Medical center/Clinic environment)..... 16

Figure 4 Block Diagram of PregSense™ Components 17

Figure 5 Schematic Illustration of the Wearable Sensory Belt 19

Figure 6 PregSense data flow of the cloud 20

Figure 7 PregSense data flow from the cloud to the App 21

Figure 8 Recording Session Flow 39

Figure 9 Pivotal study Application Flow..... 40

Figure 10 Pivotal Clinical Trial Setup Flow:..... 41

**CLINICAL STUDY EVALUATING THE SAFETY OF THE NON-INVASIVE
PREGSENSE™ AND COMPARATIVE PERFORMANCE OF PREGSENSE™
VERSUS CTG IN PRENATAL MONITORING OF PREGNANT SUBJECTS**

Ref. No.: CLP1000

Rev. 05

Page 8 of 42

STUDY SYNOPSIS

Protocol Number	CLP1000
Study Title:	Clinical Study Evaluating the Safety of PregSense™ and Comparative Performance of PregSense™ versus CTG in Prenatal Monitoring of Pregnant subjects.
Number of Centers:	Up to 5 centers with possible extension
Countries:	Israel, Germany and USA
Study Duration:	The expected total duration of the study for each subject is up to 2 hours as follows: Enrollment: Gestational age >32+0 weeks Data collection: 1 st data collection session and optional additional sessions between the initial session and up to labor.
Total Study Duration:	~24 months
Expected Subject Enrollment:	The total expected enrollment is up to 200 subjects.
Study Population:	Pregnant women with singleton gestation > 32+0 weeks of pregnancy.
Study Objectives:	The primary objective of this research is to assess the agreement between PregSense™ data collection, and values measured via the standard of care used for prenatal monitoring (i.e. CTG) and to assess the safety of PregSense™.

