9.3 Success Criterion

The study will be deemed successful if the limits of agreement (LOA's) for FHR and MHR between PregSense and the standard of care device are within the interval [-7, 7] Bpm.

In the literature, the limits of agreement for both FHR and MHR with FSE, abdominal fetal ECG and ultrasound were clinically evaluated showing that the abdominal fetal ECG limits of agreement is (± 1.96 SD) 8.40; -8.72¹¹.

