9.4 Sample Size Justification

The company intends to recruit a minimum of 50 subjects for this study. An attempt will be made to include 5 subjects with contractions per site.

The minimum recommended number of measurements for a method comparison study as per EP09-A3: "Measurement Procedure Comparison Bias Estimation Using Patient Samples Approved Guideline – Third Edition") is a sample size of 40 laboratory samples (subjects in our case). The devices will record for 30 minutes with data sampling at 1-minute intervals, i.e. each subject may have up to 30 minutes measurements of FHR and MHR available for analysis, but no less than 1 minute of paired corresponding detection data with both modalities. We expect that on average there will be at least 5 paired measurements per subject. Therefore, if at least 50 subjects are recruited for the study there will be up to 1000 measurements of heart rate with both devices and no less than 250.

¹¹ http://beijingyes.com/download/Holter_2_Accuracy_and_reliability_of_fetal_heart_rate_monitoring.pdf

In addition, from preliminary company data the mean difference between FHR measurements with two methods was 0.695BPM (SD= 1.15BPM), using the sample size equation from Lu MJ, Zhong WH, Liu YX, Miao HZ, Li YC, Ji MH (2016) Sample size for assessing agreement between two methods of measurement by Bland-Altman method. The International Journal of Biostatistics 12: issue 2 (pp. 8), we find that with a sample size of at least 50 subjects the acceptance criterion can be met at a 5% level of significance and with 90% power even if the standard deviation is almost twice as high as seen in the feasibility study.

An acceptable outcome for the secondary performance measure of Uterine contractions agreement is 85%, in order to estimate this parameter with a two-sided 95% exact binomial confidence interval having a half-width of $\pm 10\%$ at least 65 contractions are required. If each subject experience at least 2 contractions and the within subject correlation is moderate ($r=0.5$) then a sample size of 44 women will be sufficient to measure this endpoint with acceptable reliability.

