9.6.4 Performance analysis

9.6.4.1 Primary performance:

Fetal heart rate (FHR) and maternal heart rate (MHR) will both be analyzed in a similar manner as follows:

A comparison between PregSense™ measurement of FHR and MHR versus the reference measurements (i.e. CTG) are made using methods described by Bland and Altman¹².

The correlation (Pearson's correlation coefficient) and mean difference between the reference and PregSense™ measures of FHR and MHR will be presented together with a 95% confidence interval. A high correlation and a mean difference value near zero are expected if the two devices (Reference vs. PregSense™) output the same values.

In addition, a Bland-Altman plot of the mean versus the difference will be presented, and the 95% limits of agreement calculated together with respective confidence intervals. As a measure of accuracy, the mean bias and its standard deviation (with 95% confidence intervals) are estimated from random effects analysis of variance models programmed in SAS® using the MIXED procedure. This is done to accommodate the within subject correlation due to repeated FHR and MHR measurements.

Linear regression models (Deming or Passing-Bablok regression as appropriate) will be fitted to the values obtained from both devices of FHR and MHR; the slope and intercept together with respective 95% CI 's will be presented. The confidence intervals of the regression parameters will be calculated with bootstrap methodology using 10,000 simulated samples as well.

9.6.4.2 Secondary performance:

Uterine contractions as measured by PregSense™ and the standard of care (i.e. CTG including TOCO recordings), are measured continuously for a duration of 30 minutes with data sampling taken at 1-minute intervals in parallel with both study devices. We shall count the number of contractions (may be more than one per subject) as determined by the blinded assessors at each time point for which there was agreement between the PregSense™ and the standard of care. The percent of agreement (i.e. positive agreement) will be presented, the denominator of this fraction will be the standard of care number of identified contractions per subject. The binary positive agreement variable will be modeled with a

¹² https://en.wikipedia.org/wiki/Bland%E2%80%93Altman_plot

**CLINICAL STUDY EVALUATING THE SAFETY OF THE NON-INVASIVE
PRESENSE™ AND COMPARATIVE PERFORMANCE OF PRESENSE™
VERSUS CTG INPRENATAL MONITORING OF PREGNANT SUBJECTS**

Ref. No.: CLP1000

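### Section 9.6.5 judges poolability of centres on baseline variables alone and plans no unconditional centre comparison of the PregSense minus reference difference, which is the quantity being pooled

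*Combined protocol and SAP*

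**What the plan says.** Section 9.6.5 (Pooling) gives one test: "Poolability of the study centers will be evaluated by comparing the demographic and baseline parameters between the centers by data type". If centres differ significantly on those variables, "the reasons for these differences will be further explored and rationalized with reference to the effect on the main performance parameters". That follow-up depends on the baseline result and names no model, statistic or display.

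Section 9.6.4.1 estimates the bias and its standard deviation from a random effects model in SAS MIXED and states its purpose: "This is done to accommodate the within subject correlation due to repeated FHR and MHR measurements". The random effects are not listed and no centre term is mentioned. Section 9.3 sets a study-level rule, that the limits of agreement (LOAs) for FHR and MHR "are within the interval [-7, 7] Bpm".

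The Study Synopsis foresees up to five centres, possibly more, in three countries. On numbers, section 9.4 says "The company intends to recruit a minimum of 50 subjects for this study" and the Synopsis says "The total expected enrollment is up to 200 subjects".

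**The concern.** Poolability should be judged on what is pooled, here the paired difference between PregSense and the reference. Each woman is measured with both devices, so balance in age or BMI across centres says little about whether the devices agree equally well at each centre.

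Agreement can depend on things that are not baseline traits. Site staff fit the belt and the CTG transducers (section 5.1.2). Section 7.2.3 allows two CTG models and names no pulse oximeter model. The two-minute signal validation (section 5.1.2) and the exclusion of data points for poor positioning (section 9.5.1) make a large centre bias less likely, but neither measures it.

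The centres could therefore be declared poolable without anyone having examined the quantity that is pooled.

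**Working it through.** **Text.** Sections 9.3, 9.6.1, 9.6.3, 9.6.4 and 9.6.6 were read for any centre comparison of the difference. None has one. Section 9.6.5 reaches performance only after a significant baseline difference.

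**Inputs.** From section 9.4, for FHR: "the mean difference between FHR measurements with two methods was 0.695BPM (SD= 1.15BPM"), and a power claim said to hold "even if the standard deviation is almost twice as high as seen in the feasibility study". I use SD 1.15 and, as a pessimistic case, 2 × 1.15 = 2.3. There is no MHR planning figure, no per-centre enrolment and no between-centre variance. The scenario is therefore assumed: one difference per woman, five equal centres, and a constant extra bias *b* at one of them.

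**The plan's own figure.** I required the 95% confidence limits of both LOAs to lie within ±7, with SE = SD·√(1/n + 1.96²/(2(n−1))) and noncentral t power. At n = 50 and mean 0.695, power is about 1.00 at SD 1.15, 0.954 at SD 2.2 and 0.882 at SD 2.3. The largest SD that keeps 90% power is 2.28, and 2.28/1.15 = 1.98, so the claim of almost twice the SD reproduces.

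**When the odd centre leaves the margin.** Its own upper LOA exceeds 7 when b > 7 − 0.695 − 1.96·SD:
- SD 1.15: 6.305 − 2.254 = 4.05 bpm
- SD 2.3: 6.305 − 4.508 = 1.80 bpm

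For negative bias, its lower LOA falls below −7 when −b > 7 + 0.695 − 1.96·SD. At SD 1.15 that is 7.695 − 2.254 = 5.44 bpm.

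**When the pooled result fails.** With centre share p, the pooled mean is 0.695 + p·b and the pooled variance is SD² + p(1−p)b². Setting the pooled LOA, or its outer confidence limit with t(n−1), equal to the margin gives the largest bias that still passes:

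| Case | Odd centre outside from | Pooled passes to: point LOA | Confidence limits, n = 50 | Confidence limits, n = 200 |
|---|---|---|---|---|
| SD 1.15, p = 0.2, positive | 4.05 | 5.88 | 4.67 | 5.24 |
| SD 2.3, p = 0.2, positive | 1.80 | 4.02 | 1.89 | 3.00 |
| SD 1.15, p = 0.2, negative | 5.44 | 7.39 | 5.98 | 6.64 |
| SD 1.15, p = 0.3, positive | 4.05 | 4.80 | 3.84 (no window) | 4.30 |

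Section 9.3 does not say whether the point LOAs or their confidence limits must lie inside the margin, so both are shown.

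**Worked example.** Take b = 4.3, SD 1.15, p = 0.2.
- Pooled mean: 0.695 + 0.86 = 1.555
- Pooled SD: √(1.3225 + 0.16 × 18.49) = 2.069
- Pooled LOAs: −2.50 to 5.61, which pass on either reading
- The centre's own LOAs: 4.995 ± 2.254, that is 2.74 to 7.25

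**What a centre comparison could detect.** For a one-way F test on (4, n−5) degrees of freedom with noncentrality (n/5)·0.8·b²/SD² at 5%, 80% power is reached at:
- SD 1.15: 1.48 bpm (n = 50) or 0.71 bpm (n = 200)
- SD 2.3: 2.96 bpm (n = 50) or 1.42 bpm (n = 200)

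For b = 1.8 at SD 2.3, power is 35% at n = 50 and 96% at n = 200.

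**The case against.** Several points on the other side have force.

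- **The success rule is not endangered.** It is study-level, and no by-centre claim is made. This stands: the gap affects the poolability conclusion only.
- **LOAs already penalise a deviant centre.** If they use total variance, the centre shifts the mean and widens the SD. This is true, and it is why the pooled result fails once the bias is large enough. Below that point the centre goes unnoticed. The planned Bland-Altman plot might show a cluster, but no centre labels are promised.
- **Section 9.6.5 does mention performance.** It does so only after a significant baseline difference. The accurate statement is that no unconditional or specified comparison is planned.
- **A constant centre bias is speculative.** FHR comes from one central cloud algorithm (section 3.4.2), poor fit is mostly screened out, and faults could add scatter instead of an offset. The unnamed oximeter bears on MHR, while every figure here is for FHR. All of this is fair, and it is why the figures are only an illustration.
- **The windows are narrow on the confidence-limit reading**, the one that reproduces the section 9.4 power claim. At n = 50 they are 4.05 to 4.67 bpm (SD 1.15) and 1.80 to 1.89 bpm (SD 2.3), and absent for a 30% centre at SD 1.15. This also stands.
- **The remedy sets no poolability threshold.** Correct. With five or fewer centres and small numbers in each, a by-centre pass/fail rule would be unreliable.

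These points limit the seriousness of the gap but do not close it.

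**Conclusion.** The concern holds. The poolability rule examines the wrong quantity, and similar baseline with different agreement would prompt no look.

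Under the assumed scenario at SD 1.15, an extra bias between 4.05 and 5.88 bpm at one of five equal centres (4.05 to 4.67 with 50 women on the confidence-limit reading) would put that centre outside the margin while the pooled result passes. A direct centre comparison would have 80% power from 1.48 bpm, well below that range. At SD 2.3 with 50 women it would often miss a bias below about 3 bpm.

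These sizes rest on a hypothetical constant bias, equal centres and one difference per woman. The pooled estimate and the pass/fail rule are not shown to be wrong. The change should be made because it is cheap and supports a conclusion the plan intends to draw; the primary analysis does not depend on it.

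**What to change.** Amend section 9.6.5 as follows.

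1. Whatever the baseline comparison shows, compare the FHR and MHR PregSense minus reference differences between centres with the subject-level mixed model, and report bias by centre with 95% confidence intervals.
2. Show by-centre LOAs as descriptive only, with no by-centre pass/fail rule.
3. Keep the pooled LOAs on total variance (subject, residual and any between-centre component), so that a centre term cannot narrow them. In the worked example, a fixed centre effect with residual-SD limits would give 1.555 ± 2.254, that is −0.70 to 3.81, instead of −2.50 to 5.61.
4. Report any centre difference alongside the pooled conclusion, and keep the baseline comparison as descriptive.

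The cost is one table and one model comparison from data already collected. Precision is limited, as these 95% half-widths (bpm) show:

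| Women per centre | Bias, SD 1.15 | Bias, SD 2.3 | LOA, SD 1.15 | LOA, SD 2.3 |
|---|---|---|---|---|
| 10 | ±0.82 | ±1.65 | ±1.46 | ±2.91 |
| 40 | ±0.37 | ±0.74 | ±0.63 | ±1.27 |

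By-centre LOAs cannot show that a centre fails. In 200,000 simulated centres with a true upper LOA of 7.25 (b = 4.3, SD 1.15), its confidence interval lay wholly above 7 in 0.1% of centres of 10 women and 6.4% of centres of 40. The between-centre variance will also be poorly estimated with five or fewer centres.
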